7.4. Study Success Criteria

The study will be considered a success if both the primary endpoints meet their respective Performance Goals. For the effectiveness endpoint, this translates into observing a one-sided 97.5% lower confidence limit (LCL) of the point estimate above 76% and for the safety endpoint it means observing a one-sided 97.5% LCL above 80%.

7.5. Secondary Endpoints

The following secondary endpoints will be studied:

1. Change in percent stenosis after treatment with Revolution™ Peripheral Atherectomy System, determined after atherectomy and prior to other adjunctive therapies, as measured by the angiographic core laboratory
2. Procedural success as defined by target lesion residual stenosis of $< 30\%$ at the conclusion of the index procedure, after atherectomy and any adjunctive endovascular treatment, as measured by the angiographic core laboratory;
3. Assessment of the individual components of the primary safety endpoint (MAE); including all-cause mortality, major target limb amputation, clinically significant distal embolization, major target vessel perforation requiring surgical or endovascular repair, and clinically-driven TLR, measured through 30 days and at 6 months.;
4. Minor unplanned target limb amputation rate through 30 days and 6 months;
5. Myocardial infarction through 30 days and 6 months;
6. Incidence of TVR through 30 days and 6 months;

^g Technical success is defined on the post-atherectomy angiogram, prior to adjunctive therapy with balloon angioplasty, stent deployment, or any other intervention.

^h Shan, G. C. Ma. Efficient tests for one sample correlated binary data with applications. *Stat Methods Appl*, 23:175-188, 2014.

7. Frequency of angiographic procedural distal embolization (symptomatic) in the target limb as confirmed angiographically by the core laboratory;
8. Primary patency of the target lesion at 30 days and 6 months, determined by duplex ultrasound or angiography;
9. Primary-assisted patency of the target lesion at 30 days and 6 months, determined by duplex ultrasound or angiography.
10. Secondary patency of the target lesion at 30 days and 6 months, determined by duplex ultrasound or angiography.

7.6. Missing Data

Every effort will be made to minimize the amount of missing data. Recognizing the difficulty of avoiding some missing data, however, data imputation methods with sensitivity imputation analyses will be pre-specified in the Statistical Analysis Plan. Subjects with missing effectiveness data for target lesions (MLD at the conclusion of atherectomy) will be assumed to have missing data at random and will be imputed by random selection with replacement of data from target lesions with post-atherectomy measurements. The robustness of the multiple imputation outcome will be tested with a tipping point analysis encompassing all possible imputation outcomes.

7.7. Derivation of the Safety Performance Goal

The primary safety endpoint of 30-day MAE was available from the following 13 studies (**Table 2**):

Table 2. Safety Performance Goal Literature Summary

Study	Subjects	Subjects with MAE	MAE Rate (%)
Sixt ²⁵	89	14	15.7%
Zeller ²⁶	172	22	12.8%
Sundaram ²⁷	148	50	33.8%
AtheroMed Phoenix 510(k) report ²⁸	105	4	3.8%
McKinsey ²⁹	799	80	10.0%
Sixt ³⁰	161	20	12.4%
Stoner ³¹	40	4	10.0%
Zeller ³²	84	10	11.9%
Yancey ³³	17	5	29.4%
CRAG ³⁴	72	10	13.9%
Ramaiah ¹⁸	601	19	3.2%
Muck ³⁵	125	14	11.2%
Safian ³⁶	124	4	3.2%

The weighted average MAE rate was 10.1%. Using a 10% margin and rounding up to the nearest percent, the performance goal for the primary safety endpoint, 30-day freedom from MAE, is 80%.

7.8. Derivation of the Effectiveness Performance Goal

The primary effectiveness endpoint of acute technical success from atherectomy prior to adjunctive therapy was assessed from a literature review (**Table 3**). The weighted average Technical Success rate was 86.0%. Using a 10% margin and rounding up to the next percent, the performance goal for the primary effectiveness endpoint of technical success is 76%.

Table 3. Effectiveness Performance Goal Literature Summary

Study	Target Lesions	Target Lesions with Technical Success
Sixt ²⁵	89	82 (92.1%)
AtheroMed Phoenix 510(k) report ²⁸	123	117 (95.1%)
Sixt ³⁰	164	124 (75.6%)
Zeller ³²	131	126 (96.2%)
Von Polnitz ³⁷	86	70 (81.4%)
Ramaiah ¹⁸	1258	1072 (85.2%) ⁱ
Avenger Pantheris 510(k) report ³⁸	164	158 (96.3%)

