7. STATISTICS AND DATA ANALYSIS

7.1. Statistical Methodology

The objective of the statistical design for this study is to evaluate the safety and effectiveness of the study device, as assessed in comparison to literature-derived performance goals.

The safety and effectiveness performance goals were determined from a literature review of atherectomy publications. A total of 19 studies were included in this review and, among these, 13 reported data referable to the primary safety endpoint and 7 reported data referable to the primary effectiveness endpoint. Studies with populations that overlapped the population of another study were excluded.

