7.9. Sample Size

The PG of 80% has been established for the primary safety endpoint, based on a one-sided 97.5% exact binomial test. The 30-day MAE rate is anticipated to be approximately 9%. Under these assumptions, the required sample size to achieve a level of 90% power is 110 subjects (**Table 4**). Assuming 10% attrition over 30 days, initial enrollment of 121 subjects is necessary.

A PG of 76% has been established for the primary effectiveness endpoint. Anticipating an actual technical success rate of approximately 86%, and based upon a one-sided 97.5% exact binomial test, the required sample size to achieve a level of 90% power is 165 target lesions. Assuming a 1.5 ratio of subjects to treated target lesions, approximately 110 subjects will be necessary (**Table 5**). Since the primary effectiveness endpoint is determined at the time of the index procedure, no attrition has been taken into account.

ⁱ The TALON publication reported the results in 1258 target lesions, among which 132 required preliminary balloon dilatation to deliver the device and technical success ($\leq 50\%$ residual stenosis after atherectomy) was not achieved in 54 lesions. Technical success was calculated assuming there was no overlap between these cases; i.e. technical success was achieved in 1072 (1258 – 132 - 54) lesions.

Table 4. Sample Size – Primary Safety Endpoint

Primary Safety Endpoint	
Performance goal	80%
Anticipated freedom from MAE	91%
Significance level	.025
Statistical test	One-sided exact binomial test
Desired power level	90%
Required sample size prior to 10% 30-day attrition rate	110
Required sample size after attrition adjustment	121

Table 5. Sample Size – Primary Effectiveness Endpoint

Primary Effectiveness Endpoint	
Performance Goal	76%
Anticipated technical success rate	86%
Significance level	.025
Statistical test	One-sided exact binomial test
Desired power level	90%
Required sample size (target lesions)	165
Estimated subjects required for required number target lesions*	110

* Assumes 1.5 target lesions treated per subject; a ratio calculated from the studies in the atherectomy literature review

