3.3 Sample Size Consideration

This study will enroll up to 121 subjects at up to 18 investigational sites and the sample size estimation was based on binomial hypothesis testing of a single proportion.

The performance goal (PG) of 80% has been established for the primary safety endpoint. Sample size estimation was based on a one-sided 97.5% exact binomial test. The 30-day

⁴ This point is defined as entry of the study device into the access sheath/guide at the level where the sheath/guide enters the subject's body.

MAE rate is anticipated to be approximately 9%. Under these assumptions, the required sample size to achieve a level of 90% power is 110 subjects (Table 1). Assuming 10% attrition over 30 days, initial enrollment of 121 subjects is necessary.

A PG of 76% has been established for the primary effectiveness endpoint. Anticipating an actual technical success rate of approximately 86%, and based upon a one-sided 97.5% exact binomial test, the required sample size to achieve a level of 90% power is 165 target lesions. Assuming a 1.5 ratio of subjects to treated target lesions, approximately 110 subjects will be necessary (Table 2). Since the primary effectiveness endpoint is determined at the time of the index procedure, no attrition has been taken into account.

Table 1. Sample Size – Primary Safety Endpoint

Primary Safety Endpoint	
Performance goal	80%
Anticipated freedom from MAE	91%
Significance level	.025
Statistical test	One-sided exact binomial test
Desired power level	90%
Required sample size prior to attrition (subjects) adjustment*	110
Required sample size after attrition rate adjustment	121
*Assumes 10% 30-day attrition	

Table 2. Sample Size – Primary Effectiveness Endpoint

Primary Effectiveness Endpoint	
Performance Goal	76%
Anticipated technical success rate	86%
Significance level	.025
Statistical test	One-sided exact binomial test
Desired power level	90%
Required sample size (target lesions)	165
Estimated subjects required for required number target lesions*	110
*Assumes 1.5 target lesions treated/subject; ratio calculated from atherectomy literature review.	

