4.5 Study Success Criteria

The study will be considered a success if both the primary endpoints meet their respective Performance Goals. For the effectiveness endpoint, this translates into observing a one-sided 97.5% lower confidence limit (LCL) of the point estimate above 76% and for the safety endpoint it means observing a one-sided 97.5% LCL above 80%.

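### Table 3 averages to 86.8%, not 86.0%, so the protocol's own rule gives an effectiveness performance goal of 77%, not 76%

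*Protocol*

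**What the plan says.** Protocol 7.1 and SAP 4.1 describe a literature review in which "7 reported data referable to the primary effectiveness endpoint". Table 3 of the protocol prints seven rows of lesion counts and technical successes.

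From that table, protocol 7.8 states: "The weighted average Technical Success rate was 86.0" percent. It continues: "Using a 10% margin and rounding up to the next percent, the performance goal for the primary effectiveness endpoint of technical success is 76" percent.

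The SAP has no derivation of its own and refers the reader to the protocol. It takes the figure over in 3.3 ("A PG of 76% has been established for the primary effectiveness endpoint") and makes it the decision rule in 4.5: for effectiveness, "this translates into observing a one-sided 97.5% lower confidence limit (LCL) of the point estimate above 76" percent. The same 76% stands in the protocol synopsis, in 7.4, in 7.9 and in Table 5. Both primary endpoints must meet their goals for the study to succeed.

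**The concern.** The stated average does not follow from the table it is said to summarise. The gap is 0.8 points, too large for rounding: 86.0% of 2015 lesions is about 1733 successes, 16 fewer than the 1749 printed.

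The gap matters because the rule rounds up to a whole percent. An average of 86.0% lands on 76%; an average of 86.8% lands on 77%. In a single-arm study the performance goal is the only comparator, so an error in it goes straight into the success criterion. Here it lowers the bar. A result whose lower confidence limit falls between 76% and 77% would be declared a success although it misses the goal that the plan's own rule produces. The 86% planning rate for the sample size equals the misstated average, so it needs rechecking too.

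**Working it through.** **What the rule means, checked on safety.** Protocol 7.7 uses the same wording for Table 2. Pooling its 13 rows gives 256 events in 2537 subjects = 10.09%, the stated 10.1%. Freedom from MAE is 100 − 10.09 = 89.91%; less 10 points is 79.91%; rounded up, 80%, the stated goal. So the average is pooled counts and the margin is an absolute 10 points.

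**Inputs for effectiveness (protocol Table 3, in printed order).**

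| Row | Lesions | Successes |
|---|---|---|
| 1 | 89 | 82 |
| 2 | 123 | 117 |
| 3 | 164 | 124 |
| 4 | 131 | 126 |
| 5 | 86 | 70 |
| 6 (large registry) | 1258 | 1072 |
| 7 (last 510(k) report) | 164 | 158 |
| **Total** | **2015** | **1749** |

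**Reproducing the stated 86.0%.** Rows 1 to 6 alone give (1749 − 158)/(2015 − 164) = 1591/1851 = 85.95%, which rounds to 86.0%. No other single-row omission does this. Dropping rows 1 and 2 together also comes close, at 85.97%.

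**All seven rows.** 1749/2015 = 86.80%. Weighting the rounded row percentages gives 86.78%. Then 86.80 − 10 = 76.80%, which rounds up to 77% (and to 77% as the nearest percent).

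**Other weightings of the seven rows.** The unweighted mean is 88.9%, inverse-variance 90.1%, random effects 89.4% (raw scale) or 90.2% (logit scale), square-root-of-n 88.0%, approximate subject weights 87.0% to 87.3%, and logit-scale fixed effect 85.5%. None is 86.0%.

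**The registry row.** The footnote to Table 3 says "technical success was achieved in 1072 (1258 – 132 - 54) lesions", assuming that its two kinds of failure do not overlap. That is already the least favourable count. The other readings tried raise the pooled average to between 89.5% and 93.3%.

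**Effect on the test.** This uses the exact one-sided binomial at 0.025 with 165 lesions, the plan's sample-size basis. The pass mark is the smallest r with P(X ≥ r | goal) ≤ 0.025.

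| Goal | Pass mark | P(pass) at the goal | Power at true 86% |
|---|---|---|---|
| 76% | 137 (83.0%) | 1.9% | 88.5% |
| 77% | 138 (83.6%) | 2.3% | 83.9% |

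- P(X ≥ 137 | 77%) = 3.7%: the chance that a device exactly at 77% passes the rule as written.
- Against 77% with a true rate of 86.8%, power is 90.3%.
- Against 77% with a true rate of 86%, 90% power needs about 199 lesions (normal approximation) or 200 (exact test).
- The plan's 165 for 90% power is the normal-approximation result for 76% against 86%. The exact test gives 88.5%. That shortfall is separate from the Table 3 error.

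**The case against.** The arithmetic is not open to dispute. The serious objections concern what follows from it.

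First, 76% may be right for the set of studies actually averaged. Without the last row the rule gives 75.95%, which rounds up to 76%, so the fault could lie in the table and the study count. The text also says only that seven studies reported relevant data; 7.8 does not say in terms that all seven entered the average. This stands as a possible explanation, but it is inference. The row is printed in the summary table, the count of seven appears in both documents, and no exclusion is given.

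Second, the 3.7% is not a type I error for the hypothesis as written. For a null of 76% the exact rule has an actual size of 1.9%. This is correct: 3.7% becomes an error rate only once 77% is accepted as the goal.

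Third, SAP 4.3 replaces the primary effectiveness method with GEE and says that the within-subject correlation needed for a power assessment is not available. The number of lesions may also differ from 165. The pass marks and power figures are therefore indicative. The threshold for the lower confidence limit applies under any method.

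Fourth, the practical shift is small: one more success in 165. If the planning rate is corrected along with the goal, no power is lost against the 90% target. Both statements are true, but neither makes the stated average agree with its table.

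**Conclusion.** The point holds. Table 3 as printed gives 86.8%, and the protocol's own margin and rounding give a goal of 77%. The 76% used in the hypotheses, the sample size and the success criterion is one point too low for the evidence shown.

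This conclusion rests on two readings: that the average is pooled counts, which the safety derivation confirms, and that all seven printed studies belong in it, as the table and the study count indicate. The size is modest: one success in 165 lesions, and a fall in power at a true 86% from 88.5% to 83.9%, both under the exact binomial test with independent lesions. It still needs correction before analysis, because it concerns the decision threshold of a co-primary endpoint and the error favours the device.

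**What to change.** Correct the average in protocol 7.8 to 86.8%. Set the goal and the confidence-limit threshold to 77% in the synopsis, protocol 7.4, 7.8, 7.9 and Table 5, and in SAP 3.3, Table 2 and 4.5. Restate the power against 77% and say which planning rate is used: with 165 lesions, 83.9% at 86% or 90.3% at 86.8%, marked as exact-binomial figures that ignore clustering.

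If the last study was meant to be excluded, remove it from Table 3, change seven studies to six in protocol 7.1 and SAP 4.1, and give the reason. The 76% then follows from the rule.

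The cost is an amendment to both documents and a threshold one point less favourable to the sponsor. No subjects need be added if the power is restated. Restoring 90% at a true 86% would take about 200 lesions, or 200/1.5 ≈ 133 subjects. Both documents plan a descriptive look at the primary endpoints after 25 subjects, so the amendment should record whether that look had already taken place.

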7.9. Sample Size

The PG of 80% has been established for the primary safety endpoint, based on a one-sided 97.5% exact binomial test. The 30-day MAE rate is anticipated to be approximately 9%. Under these assumptions, the required sample size to achieve a level of 90% power is 110 subjects (**Table 4**). Assuming 10% attrition over 30 days, initial enrollment of 121 subjects is necessary.

A PG of 76% has been established for the primary effectiveness endpoint. Anticipating an actual technical success rate of approximately 86%, and based upon a one-sided 97.5% exact binomial test, the required sample size to achieve a level of 90% power is 165 target lesions. Assuming a 1.5 ratio of subjects to treated target lesions, approximately 110 subjects will be necessary (**Table 5**). Since the primary effectiveness endpoint is determined at the time of the index procedure, no attrition has been taken into account.

ⁱ The TALON publication reported the results in 1258 target lesions, among which 132 required preliminary balloon dilatation to deliver the device and technical success ($\leq 50\%$ residual stenosis after atherectomy) was not achieved in 54 lesions. Technical success was calculated assuming there was no overlap between these cases; i.e. technical success was achieved in 1072 (1258 – 132 - 54) lesions.

Table 4. Sample Size – Primary Safety Endpoint

Primary Safety Endpoint	
Performance goal	80%
Anticipated freedom from MAE	91%
Significance level	.025
Statistical test	One-sided exact binomial test
Desired power level	90%
Required sample size prior to 10% 30-day attrition rate	110
Required sample size after attrition adjustment	121

Table 5. Sample Size – Primary Effectiveness Endpoint

Primary Effectiveness Endpoint	
Performance Goal	76%
Anticipated technical success rate	86%
Significance level	.025
Statistical test	One-sided exact binomial test
Desired power level	90%
Required sample size (target lesions)	165
Estimated subjects required for required number target lesions*	110

* Assumes 1.5 target lesions treated per subject; a ratio calculated from the studies in the atherectomy literature review

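### The 90% safety power is conditional on an unexplained 9% MAE rate; the exact test the plan names gives about 88-89% at that rate, and about 79-80% at the protocol's own literature rate of 10.1%

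*Protocol*

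**What the plan says.** Protocol 7.9 fixes the null: "The PG of 80% has been established for the primary safety endpoint", "based on a one-sided 97.5% exact binomial test". It then gives the alternative: "The 30-day MAE rate is anticipated to be approximately 9" per cent. On these inputs it concludes that "the required sample size to achieve a level of 90% power is 110 subjects". For losses it adds: "Assuming 10% attrition over 30 days, initial enrollment of 121 subjects is necessary". Table 4 prints 91% freedom from MAE, 90% power, 110 and 121. SAP 3.3 and its Table 1 repeat the calculation, and the synopsis summarises it.

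Protocol 7.7 reports the literature behind the goal: "The weighted average MAE rate was 10.1" per cent, over the 13 studies in Table 2. A 10% margin on that average produces the 80% goal. Protocol 7.4 and SAP 4.5 set the decision rule: "for the safety endpoint it means observing a one-sided 97.5% LCL above 80" per cent, with both primary endpoints required for study success.

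For effectiveness, Protocol 7.8 states a literature average of 86.0%, and 7.9 uses 86% as the anticipated rate.

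**The concern.** The two primary endpoints are handled differently. For effectiveness, the device is expected to match the stated literature average. For safety, it is expected to do 1.1 percentage points better (9% against 10.1%), and neither document gives a reason. Protocol section 3 says the device has not been formally evaluated in the US, and no MAE rate for this device appears anywhere.

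This matters because power falls steeply with the MAE rate in this range. Study success needs both endpoints, so a lower chance of passing on safety directly lowers the chance of overall success. The plan shows power at a single rate, so a reader cannot see how much rests on it.

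Two smaller points sit beside this. The plan names an exact test, but 110 is the answer from a normal approximation. And 121 less 10% is not 110.

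**Working it through.** **Inputs.** Null p0 = 0.80 and one-sided alpha = 0.025 (Protocol 7.4, 7.9). Alternative p1 = 0.91 (Protocol Table 4). Literature MAE rate from Protocol Table 2: 256 events in 2537 subjects = 10.09%, so p1 = 0.899 at the stated 10.1%. Evaluable n = 110, enrolled 121, attrition 10% (Protocol 7.9). Event-free subjects who are not evaluable leave the denominator (SAP 4.7, 5.1).

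**Step 1: reproduce the plan's 110.** Normal approximation for one proportion:

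n = [(1.960 × √(0.80 × 0.20) + 1.282 × √(0.91 × 0.09)) / (0.91 − 0.80)]² = [(0.784 + 0.367) / 0.11]² = 109.4, rounded up to 110.

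The plan's figure is therefore recovered, with approximate power of 90.2% at 110.

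**Step 2: apply the test the plan names.** Let X be the number of subjects with an MAE. Success requires X ≤ c, where c is the largest count with P(X ≤ c | rate 0.20) ≤ 0.025. At n = 110, c = 13: the tail probability is 0.0170 at 13 and 0.0320 at 14. The limit is also 13 at n = 108 (0.0210) and n = 109 (0.0189). Power is P(X ≤ 13) at the assumed MAE rate:

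| MAE rate | n = 108 | n = 109 | n = 110 |
|---|---|---|---|
| 9% (plan) | 89.4% | 88.8% | 88.2% |
| 9.5% | 85.6% | 84.8% | 84.0% |
| 10.1% (literature) | 80.0% | 79.1% | 78.1% |

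At 9% the exact test first reaches 90% at n = 107 (90.02%). Power then drops slightly up to 110, because the permitted number of events stays at 13 while n grows.

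**Step 3: attrition.** 121 = 110 × 1.10, but 121 × 0.90 = 108.9, which leaves 108 or 109. Keeping 110 after 10% loss needs 110/0.9 = 122.2, so 123. Conversely, going from 121 to 110 is a loss of 11/121 = 9.1%. In the table, 108 and 109 have slightly more exact power than 110, so this slip costs nothing.

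**Step 4: scale of the sensitivity.** At 10.1% MAE, power is 83.9% even if all 121 subjects are evaluable. Exact 90% power is first reached at 137 evaluable, and for every larger n checked (to 259) it holds from 149. Dividing by 0.9 gives about 153 to 166 enrolled.

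**Step 5: the effectiveness comparison.** The anticipated 86% equals the average stated in Protocol 7.8. Table 3 itself sums to 1749/2015 = 86.8%, so the effectiveness alternative is no better than the literature on either figure.

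**The case against.** The strongest reply is that nothing has been miscalculated on the plan's own terms. The 90% is expressly tied to 9% in Protocol 7.9, in the synopsis and in the tables, so it is not an unqualified claim. At 9% it reproduces by normal approximation, and exact power falls short by less than two points. All of this stands.

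Next, the 10.1% sets the performance goal; it is not offered as a forecast for this device. The studies range from 3.2% to 33.8%. Treated as one sample, 256/2537 has an exact 95% interval of 8.9% to 11.3%, which includes 9%. Leaving out the study with 33.8% gives 206/2389 = 8.6%; leaving out the 601-subject registry gives 237/1936 = 12.2%. A reader might infer that the protocol's own evidence contradicts 9%. It does not: it leaves 9% unsupported. Likewise, the absence of formal US evaluation does not show that the sponsor had no other basis; it shows only that none is written down.

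On attrition, the synopsis says approximately 10%, and 9.1% is within that wording. SAP 5.1 also keeps some early leavers evaluable, for example those with an event or with a loss date at or after day 23. So the slip is a matter of consistency only.

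Finally, low power is mainly the sponsor's own risk of missing the goal and does not weaken a positive result. That is right, and it limits the seriousness. It does not remove the case for stating the figure correctly.

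**Conclusion.** The point holds as a missing justification and a mildly overstated figure. At the assumed 9% MAE, the named exact test gives 88.2% power at 110 evaluable, or 88.8% to 89.4% at 108 to 109, rather than 90%. At the protocol's pooled literature rate, power with 108 to 109 evaluable is about 79-80%, so the chance of missing the safety goal rises from about 11% to about 20%. At 9.5% it is about 85-86%.

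A reader might go further and say that the trial has 79-80% power instead of 90%, or that the attrition slip helps to cause the loss. The documents support neither. The 79-80% applies only if the true MAE rate is 10.1%, and the whole loss comes from that rate. The slip of one or two evaluable subjects costs no exact power.

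The figures assume independent subjects, the exact binomial rule in Protocol 7.4, and attrition unrelated to events. Type I error, the 80% goal and the success rule are not affected.

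**What to change.** In the synopsis, Protocol 7.9 with Table 4, and SAP 3.3 with Table 1:

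1. Restate exact power as about 88-89% at 9% MAE and about 79-80% at the literature rate of 10.1%. A line at 9.5% (about 85-86%) would show the gradient.
2. Give the basis for expecting 9%, or say that it is an assumption more favourable than the pooled literature.
3. State that 121 enrolled less 10% leaves 108-109 evaluable, or state the attrition as about 9%.

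The cost is a few changed lines and a less favourable printed figure. Enrolment, the test and the performance goal stay as they are.

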7.3. Primary Effectiveness Endpoint

The primary effectiveness endpoint is technical success, defined by $\leq 50\%$ diameter stenosis after atherectomy with the Revolution™ Peripheral Atherectomy System, prior to adjunctive therapy, as measured by the independent core laboratory on the post-atherectomy contrast angiogram. Effectiveness will be assessed for all investigator-identified target lesions in the PP analytic group and will be calculated on a per-lesion basis.

$$H_0: P_E \leq PG_E \text{ versus } H_A: P_E > PG_E$$

for technical success; even though the device performed as designed. Since the eligibility criteria are site-determined, the subject may still be included in the ITT population but the lesion would be excluded from the PP analytic group.

where P_E is the proportion of lesions with technical success, as defined by angiographically-determined $\leq 50\%$ target lesion diameter reduction on the post-atherectomy core laboratory measurement.^g The effectiveness performance goal, PGE, is technical success defined in the same manner, derived from the published literature.

The primary effectiveness endpoint will be calculated for those target lesions that fall at or below the specified acceptable reference vessel diameter of 4.0 mm, as determined by the core laboratory. Target vessels with diameters > 4.0 mm will be excluded from the analysis, since even the largest bit size (2 mm) would not result in a post-atherectomy channel size of $\geq 50\%$ RVD.

The primary effectiveness endpoint analysis will use the E+M approach for one sample correlated binary data with cluster size of one or two that accounts for correlations between multiple target lesions within the same subject.^h

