8.3. Treatment Assessment

Atherectomy using the Revolution™ Peripheral Atherectomy System is considered the treatment phase of the study. The procedure is conducted under fluoroscopic/angiographic guidance. Refer to the Instructions for Use (IFU) for techniques and methods for device deployment.

Anticoagulation therapy to ensure an activated clotting time of 250 – 300 seconds is recommended. Investigator discretion is advised regarding antiplatelet therapy and blood pressure adjustment.

Subjects who require conversion to open surgery due to treatment failure with the device will be followed at each of the follow-up visits specified in **Table 6**.

The following data are to be recorded on the subject's Treatment CRF.

- Procedure time (first cut to last stitch)
- Device runtime, passes and issues
- Description of adjunctive therapy used post-atherectomy
- Blood loss and replacement fluids (blood products) administered
- Vascular access artery
- Proximal device placement location
- Required additional procedures prior, post and/or during atherectomy procedure
- Anticoagulation use during the procedure (agent, total dose)
- AE observation, evaluation, and treatment

Table 6. Schedule of relevant assessments

Assessment	Screening/ Baseline	Treatment	Discharge	1m ± 1 week	6m ± 2 weeks	Unscheduled Visits ^j
Informed consent	Within 30 days of index procedure					
Medical history	Within 30 days of index procedure					
Verify inclusion/exclusion criteria	Within 30 days of index procedure					
Pregnancy testing for female patients of childbearing potential	Within 7 days of index procedure					
Physical examination with peripheral vascular assessment	Within 30 days of index procedure					X
Examination of access site and assessment of healing			X			
Ankle- or toe-brachial index	Within 30 days of index procedure			X	X	X
Rutherford Category	Within 30 days of index procedure			X	X	
Duplex ultrasound examination or angiography	Within 90 days of index procedure			X	X	X
Adverse event assessment		X	X	X	X	X
Patient-reported outcome questionnaires	Within 30 days of index procedure			X	X	

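### The effectiveness goal counts 132 pre-dilated lesions in its largest source as failures, but the trial endpoint has no stated rule for such lesions

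*Protocol*

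**What the plan says.** Protocol 7.8 pools seven literature sources (Table 3), states a weighted average of 86.0%, takes off 10 points and rounds up to a goal of 76%. Footnote i, attached to the largest row, explains that row: "The TALON publication reported the results in 1258 target lesions", "among which 132 required preliminary balloon dilatation to deliver the device", and the threshold of at most 50% residual stenosis "was not achieved in 54 lesions". Both groups are subtracted: "Technical success was calculated assuming there was no overlap between these cases", so "technical success was achieved in 1072" lesions.

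The trial endpoint (protocol 5.2 and 7.3; SAP 2.2 and 4.3) is core-laboratory diameter stenosis of at most 50% after atherectomy and before adjunctive therapy. Protocol 7.3 says the goal "is technical success defined in the same manner, derived from the published literature", and SAP 4.3 repeats this. Neither document prohibits pre-dilatation of a target lesion, excludes a pre-dilated lesion or scores it as a failure. The Treatment CRF list in protocol 8.3 has one item for adjunctive therapy given after atherectomy and a separate item, "Required additional procedures prior, post and/or during atherectomy procedure", with no scoring consequence.

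**The concern.** A performance goal is a fair comparator only if success means the same thing on both sides. In the source that supplies 62% of the pooled lesions, a lesion that needed a balloon before the device could be delivered is a failure whatever its residual stenosis. In the trial as written, the same lesion would be judged on residual stenosis and could be a success. That lowers the benchmark relative to the endpoint, in the device's favour. Effectiveness is one of two endpoints that must both succeed (protocol 7.4, SAP 4.5), so the mismatch bears directly on the study's pass or fail decision. If the rule stays unstated, the choice could also be made after the data are seen.

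**Working it through.** **Inputs.** Table 3 (successes/lesions): 82/89, 117/123, 124/164, 126/131, 70/86, 1072/1258, 158/164. Footnote i: 132 pre-dilated, 54 above the threshold. Protocol 7.8: 10-point margin, rounded up. Protocol 7.9: one-sided 0.025 exact binomial test, 165 lesions, anticipated success 86%.

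**The plan's own figures.**
- Largest row: 1258 − 132 − 54 = 1072; 1072/1258 = 85.2%. Reproduced.
- Pooled rate: sum of successes / sum of lesions = 1749/2015 = 86.8%, not the stated 86.0%. Less 10 points this is 76.8%, which rounds up to 77%, not 76%. Leaving out the last row gives 1591/1851 = 85.95%, which matches 86.0% and 76%. This one-point discrepancy is separate from the present issue and is kept apart below.
- Sample size: the normal approximation gives 164.3, so 165. The exact test at n = 165 against 76% needs 137 successes (83.0%), with alpha 0.0187 and power 88.5% at 86%.

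**The goal with pre-dilated lesions handled differently.**

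| Handling of the 132 | Largest row | Seven-row pool | Less 10 points | Goal |
|---|---|---|---|---|
| Failures (as tabulated) | 1072/1258 = 85.2% | 1749/2015 = 86.8% | 76.8% | 77% |
| By residual stenosis alone | 1204/1258 = 95.7% | 1881/2015 = 93.3% | 83.3% | 84% |
| Left out (no overlap) | 1072/1126 = 95.2% | 1749/1883 = 92.9% | 82.9% | 83% |

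The 1204 is 1258 − 54. On the six rows that match the stated 86.0%, the last two lines become 1723/1851 = 93.1% (goal 84%) and 1591/1719 = 92.6% (goal 83%). The handling of these lesions therefore moves the goal by 6 to 7 points from the 77% that the table supports, or by 7 to 8 points from the stated 76%.

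**Power against a matched goal.** At n = 165, a goal of 83% needs 147 successes (89.1%) and a goal of 84% needs 148 (89.7%). At a true rate of 86%, exact power is 15.0% and 10.1%.

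**Effect on false success.** Suppose true success is exactly 76% when pre-dilated lesions are failures, a fraction q of lesions is pre-dilated, all of these end at or below 50% stenosis, and the trial counts them as successes. The scored success rate is then 0.76 + q, and the pass rate is P(X ≥ 137) for X ~ Binomial(165, 0.76 + q).

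| q | Pass rate |
|---|---|
| 0% | 1.9% |
| 1% | 3.7% |
| 2% | 6.8% |
| 5% | 29% |
| 8% | 68% |
| 10.5% (= 132/1258) | 92% |

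The documents give no value of q for this device. The 10.5% is the rate in a different device's registry.

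**The case against.** The strongest reply is that there may be no mismatch. The endpoint is to be read before adjunctive balloon angioplasty, stenting or any other intervention, and a lesion ballooned before atherectomy arguably cannot meet that wording. The sponsor's own deduction suggests it may read the phrase that way. This stands as a possible reading, but the text does not establish it: the phrase fixes the timing of the angiogram, no section fails a pre-dilated lesion, and the CRF places adjunctive therapy after atherectomy.

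Two stronger inferences are tempting and should not be drawn.
- A reader might conclude that the goal should simply be 84% rather than 76%. One of those eight points comes from the separate pooling discrepancy. The rest relies on a footnote to a publication not available here, and the documents do not say how the other six sources (757 lesions) handled pre-dilatation. Correcting one row does not prove a fully like-for-like goal.
- A reader might conclude that the trial carries a false-success risk near 92%. That figure is the upper end of a scenario. It assumes another device's pre-dilatation rate, universal success in those lesions, and independent lesions, whereas SAP 4.3 now specifies GEE for clustered lesions. If few lesions are pre-dilated, the penalised and unpenalised endpoints nearly coincide.

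**Conclusion.** The concern holds as an unstated scoring rule that, with the plan followed as written, tilts the effectiveness test toward the device. For the source supplying 62% of the pooled lesions, the claim that goal and endpoint share a definition is not borne out by the text. Scoring by residual stenosis alone would put the matched goal at about 83% to 84%, against 77% from the table as it stands and 76% as stated. This rests on the footnote's count that only 54 of 1258 lesions missed the threshold.

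The inflation of the error rate cannot be fixed from the documents. It is negligible if pre-dilatation is very rare (1.9% at none), already above the nominal 2.5% at 1% pre-dilated (3.7%), and large at 5% or more, under the assumptions shown.

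Even with a matched rule, the footnote's no-overlap assumption gives the lowest possible benchmark. If all 54 lay among the 132, the row would be 1126/1258 = 89.5%, the pool 1803/2015 = 89.5%, and the goal 80%.

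**What to change.** In protocol 5.2 and 7.3 and SAP 2.2 and 4.3, state that for the test against the goal a target lesion dilated in order to deliver the study device is scored as a technical failure, matching footnote i. Report the result without this rule as supportive.

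Make sure the Treatment CRF identifies such dilatation for each target lesion, with its reason. The present item covers any procedure before, during or after atherectomy, and inflow and non-target lesions may also be treated (protocol 6.3 and 6.4), so it is not shown to isolate what is needed.

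The cost is a wording change, a check of one CRF item, and a slightly lower observed success rate if some lesions are pre-dilated.

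If the sponsor prefers to score by residual stenosis alone, the documents should say that the goal is not like-for-like and that a matched goal would be about 83% to 84%. That route is not cheap: with 165 lesions and a true rate of 86%, power against such a goal is only about 10% to 15%.
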